## 2. SYNOPSIS

Name of Sponsor/Company: Stemnion, Inc.
Name of Investigational Product: ST266 [Amnion-derived Cellular Cytokine Solution (ACCS)]
Name of Active Ingredient: ST266 (ACCS) is a novel secretome derived from proprietary cells. ST266 is composed of a complex mixture of cytokines, growth factors, nucleic acids, and undefined cellular components produced by cultured amnion-derived multi-potent progenitor (AMP) Cells in Iscove's Modified Dulbecco's Medium (IMDM). It contains at least 75 cytokines and growth factors in physiological concentrations and 2 proteins (0.5% human serum albumin and epidermal growth factor) that are added to support the growth of the cells.
Title of Study: A randomized, double-blind, placebo-controlled study to evaluate the safety, efficacy, and treatment regimen of ST266 in subjects with moderate to severe periodontitis.
Study Center(s): Multi-center (approximately 5 to 7 clinical sites in the United States)
Phase of Development: Phase 2a
Objectives: Primary: To determine the efficacy of ST266 to reduce pocket depth (PD) adjunctive to scaling and root planing (SRP). Secondary: To determine safety and changes in: 

• Clinical attachment level (CAL)

• Bleeding on probing (BOP)

Study Design: The study is a 9-month, randomized, double-blind, parallel-design study of subjects with existing moderate to severe periodontal disease randomly assigned to one of three groups. The primary endpoint of PD change will be evaluated following 9 months of treatment. Subjects will be followed for 9 months for safety and radiographic evaluations. Subjects who meet inclusion criteria will be randomized to one of three treatment groups. Randomization will be stratified by site and smoker status (never smoked or quit smoking more than two years ago vs. has smoked within the last two years). Randomization will be blocked such that assignment to treatment groups both within sites and within smoker status will be approximately even (1:1:1). Treatment will be initiated after SRP. All subjects will be evaluated at baseline and Days 1, 15, 30, 60, 90, 180, and 270.
Number of Subjects (Planned): A total of 150 subjects will be enrolled in the study, 50 per group.
Study Duration per Subject: Each subject will be enrolled in the study for 9 months.

**Diagnosis and Main Criteria for Inclusion:**

Moderate to severe periodontal disease according to American Academy of Periodontists (AAP) definition (at least 6 teeth with 6mm or greater PD and 3 mm or greater CAL at baseline).

Inclusion Criteria:

1. Provision of signed, written informed consent prior to participation in any study-related procedures.
2. Good general health as evidenced by medical history.
3. Between 18 and 85 years of age at time of informed consent signature.
4. Male or female.
5. Minimum of 18 teeth, excluding third molars.
6. Having moderate to severe periodontal disease according to AAP definition (at least 6 teeth  $\geq$ 6 mm PD and  $\geq$ 3 mm CAL at baseline).
7. Having  $>$ 30 percent bleeding sites upon probing.
8. Willing to abstain from chewing gums and other mouth rinses for the study duration.
9. Ability and willingness to attend all study visits and comply with all study visits and comply with all study procedures and requirements.
10. Willingness to abstain from routine dental care.
11. For women with reproductive potential, willingness to use highly effective contraception (e.g. licensed hormonal contraception, intrauterine device, abstinence, or vasectomy in partner).

Exclusion Criteria:

1. Presence of orthodontic appliances.
2. A soft or hard tissue tumor of the oral cavity.
3. Any dental condition that requires immediate treatment, such as carious lesions.
4. Participation in any other clinical study within 30 days of screening or during the study.
5. Pregnancy or lactation. If a subject meets this criterion, she may be rescreened for study participation when she no longer meets this criterion.
6. Antibiotic therapy within the last 30 days.
7. Chronic use ( $\geq$ 3 times/week) of anti-inflammatory medications (e.g., non-steroidal anti-inflammatory drugs, steroids). Low-dose aspirin (less than 325 mg daily) is allowed.
8. Immunocompromised subjects.
9. Subjects with cancer or a history of cancer within the last 5 years of screening.
10. Any medical history or any concomitant medication that might affect the assessment of the study treatment or periodontal tissues, such as diabetes, nifedipine, phenytoin (Dilantin), or anticoagulant medications (e.g., warfarin [Coumadin] etc.).
11. Involvement in the planning or conduct of the study.
12. History of any clinically significant disease or disorder which, in the opinion of the investigator, may either put the subject at risk because of participation in the study, or interfere with interpretation of the subject's study results.
13. Previous randomization for treatment in the present study.

Investigational product, dosage and mode of administration: 1X ST266 applied in a dose of 20 microliters per tooth. Total daily dose will be less than 1 milliliter. ST266 will be applied directly to the marginal gingiva around each tooth (buccal and lingual) using sterile packaged pipette tips compatible with the Eppendorf Repeater M4 device.

Duration of Treatment:
 
Group 1: ST266 dosed daily on Days 1-5, 8-12, 22, and 30, and then monthly for 7 months (Days 60, 90, 120, 150, 180, 210, and 240).
 
Group 2: ST266 dosed 2x/week (with at least one day between treatments) for the first 3 months and monthly for 5 months thereafter (Days 120, 150, 180, 210, and 240).
 
Group 3: Placebo dosed at the same frequency as Group 1.

Placebo, Dosage, and Mode of Administration: Sterile saline (0.9% NaCl) will be applied in the same manner and in the same volume as the investigational product, ST266.

Criteria for Evaluation:
 
Efficacy: The primary efficacy endpoint of this study is the average change in each patient between the PD at baseline and the PD at 9 months (Day 270) for those pockets <math>\geq 6</math> mm at baseline.
 
Secondary efficacy endpoints of this study are: (1) change from baseline in CAL at 9 months (Day 270); (2) change from baseline in BOP at 9 months (Day 270); and (3) change from baseline in PD at 9 months (Day 270) using all tooth-sites.
 
Exploratory endpoints of this study are: (1) Pro-inflammatory mediators, enzymes, and bone markers will be measured in gingival crevicular fluid (GCF) and serum at the baseline, Days 15, 90, 180, and 270; (2) microbial analysis of periodontal flora will be performed at baseline and at Days 15, 90, 180, and 270; and (3) change from baseline in radiographic bone levels (RBL) at Days 90 and 270; (4) FMPI analyzed at Days 90, 180 and 270; and (5) change from baseline in PD, CAL and BOP will be analyzed on Days 90 and 180.
 
Safety: The safety endpoints are frequency and pattern of adverse events (AEs) and serious adverse events (SAEs).


Planned Sample Size: The sample size for the study is based on the sample size required to reject the null hypothesis for the primary efficacy endpoint.
 
The number of subjects was estimated based on 2 meta-analysis studies that reviewed 50 and 72 articles respectively (Bonito, 2005) to reach a significant difference in PD reduction at 9 months compared with placebo.
 
Using the normal approximation for sample size determination for 2 independent samples, t-tests, and assuming a PD reduction of 0.5 mm on average (difference in means) with a standard deviation of 0.7 mm, <math>\alpha=0.05</math> (0.025 per comparison), and 85% power, a sample size of 44 per group will be required. The expected dropout rate is 20% based on previous experiments; hence 50 subjects will be enrolled per group. Generalized estimating equations (GEE) analyses will be performed and therefore, the actual power will be between 85 and 90%.

Statistical methods: Analysis of the clinical efficacy data will consist of modeling endpoints, including change from baseline in PD, CAL, BOP, and FMPI, with treatment group as a main effect and adjusting for baseline values of a given endpoint. Post-baseline treatment comparisons will be modeled through a GEE method (with a linear link and exchangeable covariance matrix), adjusting for the baseline value. Methods of analysis for periodontal flora, inflammatory cytokine levels in GCF and in serum, and RBL will be described in separate statistical analysis plans. Results will be considered significant if <math>p < 0.05</math>.

#### 4. LIST OF ABBREVIATIONS AND DEFINITIONS OF TERMS

The following abbreviations and specialist terms are used in this study protocol.

**Table 1: Abbreviations and Specialist Terms**

Abbreviation or Specialist Term	Explanation
AAP	American Academy of Periodontists
AE	Adverse event
AMP	Amnion-derived multi-potent progenitor cells
BOP	Bleeding on probing
CAL	Clinical attachment level
CEJ	Cemento-enamel junction
eCRF	Electronic case report form
FDA	Food and Drug Administration
FMPI	Full-mouth plaque index
GCF	Gingival crevicular fluid
GCP	Good Clinical Practice
GEE	Generalized estimating equation
HbA1c	Glycated hemoglobin
ICH	International Council for Harmonisation
IEC	Independent ethics committee
IL	Interleukin
IMDM	Iscove's Modified Dulbecco's Medium
IND	Investigational New Drug Application
IRB	Institutional review board
IWRS	Interactive web response system
MMP	Matrix metalloproteinase
PD	Pocket depth
PGE2	Prostaglandin E2
RBL	Radiographic bone level
SAE	Serious adverse event
SAR	Suspected adverse reaction
SRP	Scaling and root planing
ST266	Study drug: amnion-derived cellular cytokine solution

## 5. INTRODUCTION

Periodontal disease is a problem affecting millions of Americans and one for which adequate therapy is lacking. In periodontitis, an acute inflammatory reaction occurs and, if unresolved with failure of return of tissue to homeostasis, there is neutrophil-mediated tissue destruction, and inflammation becomes chronic. Although infection by Gram-negative bacteria such as *Porphyromonas gingivalis* is considered to be the primary etiologic factor in periodontal disease, the cause-and-effect relationship between the pathogen and disease is not clear. What is clear, however, is that a biofilm develops and left unchecked, tissue and bone of the periodontium are destroyed. To reduce the inflammatory response in tissues, drugs such as non-steroidal anti-inflammatory agents have been used with limited long-term success. Antibiotic therapy may provide a short-term benefit without a long-term solution. ST266 offers a novel alternative mechanism for treatment of periodontal disease.

### 5.1. Trial Rationale

Resolution of inflammation may reduce injury, promote healing, and return tissue homeostasis. Rapid elimination of the invading leukocytes from a lesion is the desired outcome following an inflammatory event. This task becomes more formidable when the acute inflammatory response progresses to chronic inflammation with destruction of the cellular matrix, scarring, and fibrosis. Thus, an essential goal for intervention in inflammatory disease is the return of tissue homeostasis (Serhan, 2011). Interventions in the management of periodontitis such as root planing offer some benefit in removing etiologic agents associated with inflammation and thereby arrest to some degree the periodontal disease; however, such procedures do not resolve the inflammation and restore tissue homeostasis. Without restoration of tissue homeostasis, inflammatory cells having pro-inflammatory products, such as prostaglandin E2 (PGE2), persist causing swelling, irritation, pain, collagen destruction, and ultimately bone resorption (Kantarci, 2006). Agents that stimulate the resolution of inflammation may offer some therapeutic advantage in the treatment of periodontitis compared with more traditional pharmacologic interventions.

### 5.2. Experience with ST266

ST266, in some ways, may be ideally suited for treating periodontitis. ST266 has been shown in *in vitro* experiments to reduce the amount of inflammatory cytokines, specifically PGE2. In *in vivo* experimental models of periodontitis in rabbits, employed to evaluate the effect of ST266 on periodontal disease, there was a marked reduction in the inflammation with the use of ST266. Furthermore, there was restoration of lost bone with histological evidence of resolution of the inflammatory infiltrates.

In a phase 1 study of gingivitis, a related disease, 54 subjects (18 per arm) were treated. Subjects had a modified gingival index score of 2.0 or greater and >40% bleeding sites at initial presentation. Three (3) cohorts were tested: Two (2) different ST266 concentrations (1X and 0.3X ST266) were compared with the saline placebo control cohort. Subjects received daily 20 µL topical treatments per tooth for 10 days administered over 2 weeks (560 µL maximum dose). A follow-up visit was conducted at Day 42 for clinical measurements and safety analysis.

Efficacy results of the phase 1 study are summarized in Table 2. Statistically significant changes in clinical attachment level (CAL) and pocket depth (PD) were observed relative to placebo for both the 0.3X and 1X ST266 treatment groups at Day 42 ( $p < 0.05$ ). Furthermore, pro-inflammatory cytokine biomarkers, interleukin (IL)-1 $\beta$  and IL-6, were significantly decreased in both the 0.3X and 1X ST266 treatment groups relative to placebo at Day 12 ( $p < 0.05$ ). These findings suggest that ST266 has a beneficial effect in subjects with gingivitis and supports prior studies demonstrating anti-inflammatory properties of ST266 mediated via modulation of pro-inflammatory cytokines.

**Table 2: ST-04-13 Efficacy Outcomes**

	Mean Difference	95% Interval	Confidence	p-value
Probing Depth (mm) day 42				
0.3X ST266 minus placebo	-0.13	-0.23	-0.04	0.005*
1X ST266 minus placebo	-0.13	-0.23	-0.03	0.008*
Clinical Attachment Level (mm) day 42				
0.3X ST266 minus placebo	-0.17	-0.28	-0.06	0.002*
1X ST266 minus placebo	-0.20	-0.31	-0.08	0.001*
Crevicular Fluid IL-1<math>\beta</math> day 12				
0.3X ST266 minus placebo	-0.24	-0.44	-0.04	0.021*
1X ST266 minus placebo	-0.25	-0.45	-0.05	0.015*
Crevicular Fluid IL-6 day 12				
0.3X ST266 minus placebo	-0.38	-0.65	-0.11	0.005*
1X ST266 minus placebo	-0.35	-0.57	-0.12	0.002*

\* Significant difference  $p < 0.05$  using GEE analysis (adjusted for baseline)

No significant safety issues were identified in the phase 1 study. Safety parameters were compared for both ST266 treatment groups (1X and 0.3X) relative to placebo using appropriate statistical methods. This included adverse events (AEs), vital signs, and oral cavity examination results. One serious adverse event (SAE; assault-fractured cheek bone, laceration) occurred during this study that was clearly not related to the study protocol or study product. There were 125 AEs/oral cavity exam findings reported during the entire study, all of which were categorized as mild. Out of 125 events, 3 (2.5%) were categorized as related, 5 (4%) were categorized as possibly related, and 5 (4%) were categorized as unlikely related. All related and possibly related events were reported by the same two subjects, both of whom were assigned to placebo. These results suggest that ST266 was safe and was well tolerated by subjects with gingivitis when administered at the 0.3X and 1X concentrations for at least 10 days of treatment.

Periodontitis with severe bony destruction remains the primary cause of tooth loss. ST266 has been shown to be profoundly anti-inflammatory in both *in vitro* and *in vivo* preclinical experiments including an accepted rabbit model of periodontitis. These findings, coupled with the excellent safety profile for ST266 in both animal testing and a phase 1 clinical trial as well as use of ST266 in topical dermal and topical ocular trials in more than 90 subjects, support the proposed clinical investigation of ST266 in the treatment of periodontal disease.

## **6. TRIAL OBJECTIVES AND PURPOSE**

### **6.1. Primary Objective**

The primary objective is to determine the efficacy of ST266 to reduce pocket depth (PD) as an adjunctive to scaling and root planing (SRP).

### **6.2. Secondary Objectives**

The secondary objectives of this study are to determine: (1) safety as established by assessment of AEs and SAEs, and (2) changes in the following clinical parameters:

- Clinical attachment level (CAL)
- Bleeding on probing (BOP)

## **7. INVESTIGATIONAL PLAN**

### **7.1. Overall Study Design**

The study is a 9-month, randomized, double-blind, placebo-controlled, parallel-design study of subjects with existing moderate to severe periodontal disease. The study design and duration is similar to the study design with previous compounds, e.g. Minocycline Microspheres, chlorhexidine chip, and others. Subjects will be recruited at multiple treatment sites. All subjects will be treated by a dental professional at the study site. The dental professional will be a qualified and trained licensed periodontist, dentist, or dental hygienist skilled in periodontal clinical research. All investigators will be trained in grading clinical parameters in the same manner for consistency. After signing informed consent, subjects will be screened with a medical and dental history and full mouth dental examination. Clinical parameters will be recorded including PD, CAL, and BOP. Subjects will have urinalysis in addition to blood tests including hematology and chemistry (liver and kidney function) panels. Women of child-bearing potential will be administered a pregnancy test.

If inclusion/exclusion criteria are met, subjects will undergo a baseline visit with measurements of FMPI, collection of gingival crevicular fluid (GCF), and blood samples. Subgingival plaque samples will be collected for microbial analysis. Vertical bitewing X-rays will be collected to assess RBL. Subjects will undergo SRP procedure(s) prior to being randomly assigned to 1 of 3 treatment groups indicated in Section 7.3. Local anesthesia must be used for SRP. All treatments of ST266 or placebo will be administered in office by a dental professional.

All subjects will be evaluated at screening, baseline, and Days 1, 15, 30, 60, 90, 180, and 270. Evaluations will be performed by a blinded dental professional to mask the group as all groups do not have the same study schedule. The blinded examiners will be independent from the dental professionals who apply the study drug to the subjects, thereby ensuring that the treatment assignment cannot be inferred based on the treatment schedule.

At each evaluation, medical and dental history will be updated, an oral exam will be performed, and AEs and SAEs will be assessed and recorded. PD, CAL, and BOP will be evaluated at screening and on Days 15, 30, 60, 90, 180, and 270. Subjects will have urinalysis in addition to blood tests including hematology and chemistry (liver and kidney function) panels done at screening and repeated at Days 90 and 270. FMPI will be recorded at baseline and on Days 15, 30, 60, 90, 180, and 270. Inflammatory cytokines in serum will be measured at baseline and on Days 15, 90, 180, and 270. GCF will be collected and analyzed at baseline and on Days 15, 90, 180, and 270. Microbial analysis of periodontal flora will be performed at baseline and on Days 15, 90, 180, and 270.

At each treatment visit, in addition to administration of ST266 or placebo, medical and dental history will be updated, AEs and SAEs will be assessed and recorded, concomitant medications will be recorded, and oral hygiene instruction will be provided.

Randomization will be stratified by site and smoker status (never smoked or quit smoking more than two years ago vs. has smoked within the last two years). Randomization will be blocked such that assignment to treatment groups both within sites and within smoker status will be

approximately even (1:1:1). ST266 will be supplied to the study site and prepared for use by trained clinical staff, who will not be the same as the dental professionals evaluating the subjects.

**Primary Endpoint:** The primary effectiveness endpoint of this study is the average change in PD from baseline to 9 months (Day 270) in tooth-sites with baseline PD  $\geq$  6mm. This endpoint will be analyzed at the patient level similar to other studies.

**Secondary Endpoints:** Secondary efficacy endpoints of this study are: (1) change from baseline in CAL at 9 months (Day 270) with baseline PD  $\geq$  6mm; (2) change from baseline in BOP at 9 months (Day 270) using whole-mouth average, and (3) change from baseline in PD at 9 months (Day 270) using all tooth-sites.

Baseline refers to the initial measurement of the endpoint, which may occur at the screening or baseline visit according to the schedule of assessments.

**Safety Endpoints:** The safety endpoints are frequency and pattern of AEs and SAEs.

**Exploratory Endpoints:** Pro-inflammatory mediators, enzymes, and bone markers will be measured in GCF and serum at baseline and on Days 15, 90, 180, and 270. Microbial analysis of periodontal flora will be performed at baseline and on Days 15, 90, 180, and 270. Change from baseline in RBL will be measured at Days 90 and 270. All x-rays for RBL will be read at a central location using predefined criteria. PD, CAL and BOP will also be analyzed at Days 90 and 180. FMPI will also be analyzed at Days 90, 180 and 270.

## 7.2. Number of Subjects

One hundred and fifty (150) subjects will be enrolled. The sample size for the study is based on the sample size required to reject the null hypothesis for the primary efficacy endpoint which contains two comparisons. Using the normal approximation for sample size determination for two independent samples, t-tests, and assuming a PD reduction of 0.5 mm on average (difference in means) with a standard deviation of 0.7 mm,  $\alpha=0.05$  (Bonferroni corrected,  $\alpha$  0.025 per comparison), and 85% power, a sample size of 44 per group will be required. The expected dropout rate is 20% based on previous experiments and current enrollment trends hence 50 subjects will be enrolled per group. GEE analyses will be performed and therefore, the actual power will be between 85 and 90%.

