### **8.4. Subject Withdrawal Criteria**

Subjects may voluntarily withdraw from the study, or be removed from the study at the discretion of the investigator or sponsor at any time. If such withdrawal occurs, or if the subject fails to return for visits, the investigator should determine the primary reason for a subject's premature withdrawal from the study and record the reason in the subject's study records.

All subjects prematurely discontinuing from the trial, regardless of cause, should be scheduled as soon as possible for a follow-up safety visit, which will include all assessments planned for Day 270 (end of study).

For subjects who are lost to follow-up (i.e., those subjects whose status is unclear because they fail to appear for study visits without stating an intention to withdraw), the investigator should document all steps taken to contact the subject, e.g., dates of telephone calls, registered letters, etc.

Subjects who are withdrawn from the study after beginning treatment will not be replaced.

---

 For the purposes of subject exclusion, *diabetes* is defined as any subject with (i) a history of type 1 or type 2 diabetes, (ii) prior or concomitant prescription of diabetes medications, or (iii) a laboratory test for glycated hemoglobin  $\geq 6.5$ .

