#### **13.2. Prevention and Treatment of Missing Data**

Efforts will be made by the sponsor and investigators to maximize subject compliance with the study protocol. Previous studies of adjunctive treatments for periodontitis reported subject completion rates  $>90\%$  (Paquette, 2004). Because this study requires a significant number of in-office treatments, a more conservative estimate of a 20% dropout rate has been made, which is reflected in the sample size calculation (Section 7.2).

Missing data in this study will be treated according to standard practices based on published recommendations of the National Research Council Panel on Handling Missing Data in Clinical Trials (National Research Council, 2010). Methods for imputation of missing data are provided in the statistical analysis plan.

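### The protocol's 50 per group does not follow from 44 evaluable and 20% dropout (44/0.80 = 55), and the SAP uses about 10% for the same 44 and 50

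*Protocol*

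**What the plan says.** Protocol section 7.2 assumes a 0.5 mm difference in mean PD reduction, an SD of 0.7 mm and a Bonferroni alpha of 0.025 for each of two comparisons with placebo. It concludes: "85% power, a sample size of 44 per group will be required". It then says: "The expected dropout rate is 20% based on previous experiments and current enrollment trends hence 50 subjects will be enrolled per group". The synopsis repeats the step: "The expected dropout rate is 20% based on previous experiments; hence 50 subjects will be enrolled per group". Both places add a power claim; in 7.2 it reads "GEE analyses will be performed and therefore, the actual power will be between 85 and 90" percent.

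Section 13.2 presents the 20% as deliberate. It notes "Previous studies of adjunctive treatments for periodontitis reported subject completion rates" above 90%, but because this trial needs many in-office treatments, "a more conservative estimate of a 20% dropout rate has been made, which is reflected in the sample size calculation".

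On replacement, section 8.4 says "Subjects who are withdrawn from the study after beginning treatment will not be replaced". Section 9.4 allows replacement only of subjects discontinued between randomization and first treatment.

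The SAP (section 2, Planned Sample Size, and section 2.6) has the same difference, SD, alpha, power, 44 and 50, but puts expected dropout at about 10%. It does not carry the GEE power sentence.

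**The concern.** There are three linked problems.

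- **Arithmetic.** The protocol presents 50 as the consequence of 44 and 20%. It is not, so the statement in 13.2 that the sample size reflects the 20% is also untrue as written.
- **Conflict.** The two governing documents give different dropout rates for the same sample size, and both cite previous experiments as the basis.
- **Unsupported power.** The protocol attributes 85 to 90% power to the use of GEE. Neither document states the variance explained by covariates, the number of tooth-sites per subject or the within-subject correlation, so the claim cannot be checked.

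What is at stake is how the result is read. If either regimen gives a null or borderline result, readers will judge it against 85 to 90% power, and the protocol's own inputs do not deliver that for an unadjusted completer comparison.

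**Working it through.** **Inputs.** Difference 0.5 mm, SD 0.7 mm, alpha 0.025 per comparison, 85% power (protocol 7.2); two-sided testing (SAP section 3); equal allocation (protocol 7.1); dropout 20% (protocol synopsis, 7.2, 13.2) or about 10% (SAP 2 and 2.6).

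**Step 1: reproduce the 44.** Normal approximation:

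n = 2 × (z0.9875 + z0.85)² × (SD/difference)² = 2 × (2.2414 + 1.0364)² × (0.7/0.5)² = 42.1, so 43.

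The noncentral t calculation gives 84.6% power at 43 and 85.5% at 44, so 44 is the t-test answer. The stated figure holds.

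**Step 2: allow for dropout.** Enrolled = evaluable/(1 − dropout).

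- 20%: 44/0.80 = 55 per group, 3 × 55 = 165 in total, 15 more than planned.
- 10%: 44/0.90 = 48.9, so 49; 50 covers it.
- Largest dropout at which 50 still leaves 44: 1 − 44/50 = 12%.
- The common mistake of multiplying, 44 × 1.20 = 52.8, gives 53, so it does not explain the 50 either.

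**Step 3: power with what remains.** Completers are 50 × 0.80 = 40, or 50 × 0.90 = 45. By normal approximation, power = Φ[(0.5/0.7) × √(n/2) − 2.2414]. For n = 40 this is Φ(3.194 − 2.241) = Φ(0.953) = 83.0%.

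| Completers per group | Power, t-test | Power, normal |
|---|---|---|
| 40 (20% dropout) | 81.6% | 83.0% |
| 44 (12% dropout) | 85.5% | 86.6% |
| 45 (10% dropout) | 86.4% | 87.4% |
| 50 (no dropout) | 90.0% | 90.8% |

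**Step 4: what would restore the stated power** (t-test / normal). If covariates explain a share R² of the variance, the residual SD is 0.7 × √(1 − R²).

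- 40 completers: 85% power is reached for a difference of 0.52 / 0.51 mm. For 0.5 mm it needs a residual SD of 0.671 / 0.682, that is R² of about 8% / 5%. Reaching 90% needs 0.624 / 0.635, that is R² of about 20% / 18%.
- 45 completers: 85% power is reached for 0.49 / 0.48 mm. Reaching 90% needs a residual SD of 0.664 / 0.673, that is R² of about 10% / 8%.

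Such values are possible, since the model in SAP 8.3.1 adjusts for baseline PD, site and smoking. But that model uses only Day 270 records, so it gains nothing from repeated visits. It also contains a smoking-by-treatment term whose effect on precision depends on a smoker share that is not stated. The 85 to 90% claim is therefore undocumented, not shown to be false.

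**The case against.** **Completer power is not the power of the primary analysis.** This stands. The primary analysis is ITT (SAP 8.3), and SAP 8.1.1 keeps dropouts by carrying the worst observation for each pocket. Protocol 8.4 also schedules early discontinuers for a visit with the Day 270 assessments, although a visit outside the Day 270 window is not a Day 270 record under SAP 8.1.4. ITT power could lie on either side of 82%. With all 50 retained and no dilution it is 90.0% by t-test. If the 20% who drop out contributed no treatment difference (an assumption: 0.8 × 0.5 = 0.4 mm, SD still 0.7) it is about 72%. The protocol's own sizing, however, treats dropout as loss of evaluable subjects, so the completer calculation is the right check of that step.

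**The shortfall is small for a Phase 2a trial.** True: 2 to 3 points, or 0.01 to 0.02 mm in detectable difference. This limits the importance of the point but does not make the step correct.

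**The 85 to 90% may simply be the range from 44 to 50 evaluable.** The t-test figures, 85.5% and 90.0%, fit that reading. But the text gives GEE as the reason, and at 20% dropout neither 44 nor 50 subjects remain.

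**Replacement could make up the loss.** Only before first treatment. The documents do not split the 20%, but 13.2 ties it to the burden of in-office treatments, so most of it would fall after treatment starts. Replacement is unlikely to close the gap.

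**The SAP's 10% has the weaker support.** Fair. Protocol 13.2 considers completion above 90% in previous studies and deliberately departs from it. A sponsor who settles on 10% should say why that reasoning no longer applies.

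**Conclusion.** The point holds and should be fixed. The 44 per group is sound; the step from 44 and 20% to 50 is wrong. The correct result is 55 per group, and 50 leaves 40 completers with 81.6% (t-test) or 83.0% (normal) power per comparison. The SAP's version is internally consistent, so the arithmetic error and the GEE claim are in the protocol only, while the 20% against 10% conflict lies between the documents. Nothing elsewhere reconciles them.

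These power figures assume the stated 0.5 mm and 0.7 mm, equal groups, no covariate adjustment and dropouts removed from the comparison. They are not the power of the ITT analysis, for which the documents give no inputs. Alpha, the endpoint and the analysis model are unaffected.

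**What to change.** Keep 150 subjects and have the sponsor choose one dropout rate for both documents.

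- **If 20%:** in the protocol synopsis and 7.2, keep 44 only as the number needed for 85% power. State that 50 enrolled gives about 40 completers and about 82% power for 0.5 mm (or 85% for about 0.52 mm) in an unadjusted completer comparison. Correct the 10% in SAP 2 and 2.6. Section 13.2 can then stand.
- **If about 10%:** state about 45 completers and about 86% power. Correct the 20% in the synopsis, 7.2 and 13.2, and give the reason for the lower rate.

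In either case:

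- Delete the GEE power sentence from the synopsis and 7.2, or support it with stated values for variance explained, tooth-sites per subject, within-subject correlation and smoker share.
- Say that the primary ITT analysis keeps dropouts by worst-value imputation, so completer power is not its power. If an ITT range is given, vary both the diluted effect and the SD.

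Holding 85% at 20% dropout would instead take 165 subjects; the text correction avoids that.

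**Cost:** text edits only, with no extra patients and no change to the model. Protocol changes need IRB review and approval before implementation (protocol 14.3). The stated power becomes less favourable, most clearly under 20%.
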